1. INTRODUCTION

The purpose of this reporting and analysis plan (RAP) is to describe the analyses to be included in the Clinical Study Report for Protocol:

Revision Chronology:		
2012N155299_00	2013-DEC-26	Original
2012N155299_01	2014-MAR-01	Amendment No. 1. Country specific Amendment for the United Kingdom to address required changes per MHRA. Updated Exclusion Criteria to exclude subjects with current corneal disease or history of corneal disease. Updated QTc withdrawal criterion to modify QTc withdrawal for QTc >500msec and to include > 60 msec increase from baseline. Updated Data Management Section 12 to include details on dissemination of data and communication plan.
2012N155299_02	2014-MAR-20	Amendment No. 2. Global Amendment to address required changes per the FDA. Updated Inclusion Criteria with minimum weight requirement. Updated Blood Volumes. Revised Time and Events Tables. Corrected typographical errors.
2012N155299_03	2014-MAY-05	Amendment No. 3. Country specific Amendment for Canada to address required changes per Health Canada. Updated preparation instructions of GSK2857916.
2012N155299_04	2016-MAY-05	Amendment No. 4. Global Amendment to include patient reported outcome instruments in the Part 2 multiple myeloma cohort and refine the lymphoma histologies eligible in Part 2 BCMA-expressing lymphoma cohort. Additionally, the requirement for 60% of tumor cells staining positive for BCMA expression was removed. The total number of subjects that may be enrolled is presented by a range of 80 to 95 to provide an updated estimate based on the number of subjects who enrolled at the time of the amendment. Additional modifications include: changing the time-point specific blood specimens are collected for baseline/pre-treatment immunogenicity and biomarker measurements, and the visit window for certain assessments.
2012N155299_05	2017-NOV-02	Global amendment to include additional follow up of multiple myeloma subjects for ocular exams (for those whose corneal signs or symptoms have not resolved), additional patient reported outcome instruments, addition of time-to-event endpoints as exploratory objectives. Subjects who have completed treatment or the 3 month follow up visit (end of study) prior to amendment 5 will be reconsented for further follow up and survival status. Other administrative changes are also included

2. SUMMARY OF KEY PROTOCOL INFORMATION

2.1. Changes to the Protocol Defined Statistical Analysis Plan

Changes from the originally planned statistical analysis specified in the protocol are outlined in [Table 1](#).

Table 1 Changes to Protocol Defined Analysis Plan

[figure not shown]
Protocol	Reporting & Analysis Plan	
Statistical Analysis Plan	Statistical Analysis Plan	Rationale for Changes

 Time to response (TTR) is defined as the time between the date of first dose and the first documented evidence of response (PR or better). Subjects without confirmed response (PR or better) will be censored at the censoring date for TTP. 	
 Time to response (TTR) is defined as the time between the date of first dose and the first documented evidence of response (PR or better), among subjects who achieve a response (i.e., confirmed PR or better). 	
 To be consistent with GSK Integrated Data Standards Library (IDSL) standard

 Time to best response (TTBR) analyses was not planned. 	
 Time to best response (TTBR), defined as the time between the date of first dose and the best response (PR or better), among subjects who achieve a response (i.e., confirmed PR or better), was added as an exploratory endpoint. 	
 To further evaluate clinical activity of GSK2857916.

 The 'Pharmacokinetic (PK) Population' is defined as those subjects in the "All Treated" population from whom at least one PK sample was obtained, analyzed, and was measurable. 	
 All subjects in the 'All Treated' population who had at least 1 non-missing PK assessment (Non-quantifiable [NQ] values will be considered as non-missing values). 	
 To be consistent with the latest GSK (IDSL) standard.

 Descriptive statistics (mean, standard deviation, median, range) will be used to summarize observed laboratory values and change from baseline in observed value at each scheduled visit, as appropriate 	
 Descriptive statistics (mean, standard deviation, median, range) will be used to summarize change from baseline in observed value at each scheduled visit, as appropriate 	
 To be consistent with the latest GSK (IDSL) standard.

2.2. Study Objective(s) and Endpoint(s)

Objectives	Endpoints
Primary Objectives	Primary Endpoints

 To determine safety, tolerability, maximum tolerated dose (MTD), and recommended phase (RP2) dose and schedule of GSK2857916 administered 	
 Adverse events (AE) and changes in clinical signs and laboratory parameters
Secondary Objectives	Secondary Endpoints

 To evaluate the pharmacokinetic (PK) profile of GSK2857916 and the breakdown product cys-mcMMAF after intravenous (IV) single and repeat dose administration in subjects with relapsed/refractory MM and BCMA expressing lymphomas 	
 GSK2857916 and cys-mcMMAF PK parameters following IV single and repeat dose administration during dose escalation as data permit (e.g., AUCs C_{max}, t_{max}, CL, V_{ss}, t_{1/2} [single dose], C_{max} and C_{trough} [repeat dose]). GSK2857916 population PK parameters in expansion cohorts at the RP2 dose (e.g. clearance (CL), volume of distribution (V_d)), and relevant covariates which may influence exposure (e.g. age, weight, or disease-related covariates e.g. BCMA expression)

 To assess anti-drug antibody (ADA) formation after IV single and repeat dose administration of GSK2857916 	
 ADA incidence and titers after single and repeat IV dosing of GSK2857916

 To explore the initial anti-tumor activity of GSK2857916 in subjects with relapsed/refractory MM and BCMA expressing lymphomas 	
 Clinical activity measured as Overall Response Rate (ORR) which is defined as follows: 
 For MM: the percentage of subjects achieving confirmed partial response or better (≥PR) In addition, the percentage of subjects with minimal response (MR) will be assessed for clinical benefit rate (CBR) (Appendix 1 of protocol) For Lymphomas: the percentage of subjects achieving PR or better (≥PR) (Appendix 2 of protocol)
Exploratory Objectives	Exploratory Endpoints

 To evaluate PD markers in MM after treatment with GSK2857916 	
 sBCMA levels, BCMA receptor occupancy and cell death markers in subjects with MM.

 To explore relationships of GSK2857916 plasma concentrations/exposure with pharmacodynamics (PD), safety and clinical activity 	
 Relationship between receptor occupancy, tumor cell death markers, sBCMA and GSK2857916 plasma PK parameters; Relationship between safety/clinical activity (e.g. ORR) and GSK2857916 PK parameters

 To characterize the relationship between clinical response and other biologic tumor characteristics (DNA, protein analysis) 	
 BCMA expression levels on malignant cells as measured by IHC and/or flow cytometry in tumor tissue, serum sBCMA levels and their relationship to clinical response

 To investigate the relationship between genetic variants in the host and response to study medicine, or susceptibility, severity and progression of disease 	
 Relationship between host genetic variation and response to study medicine or susceptibility, severity and progression of disease

Objectives	Endpoints

 To explore the effect of GSK2857916 on symptoms (including bone pain, fatigue and visual symptoms) and impacts on HRQoL in subjects with relapsed/refractory MM (Part 2) 	
 Changes from baseline in bone pain/fatigue and analgesic use as measured by the eDiary Interviews with subjects to further characterize changes in symptoms (including bone pain/, fatigue and visual symptoms) and impacts on HRQoL

 To explore changes in visual symptoms and function following discontinuation of treatment with GSK2857916 	
 Changes in visual symptoms and impacts as measured by the OSDI and NEI-VFQ-25 following treatment discontinuation Follow-up telephone interviews conducted to further understand subjects experience with visual symptoms and changes in symptoms and related impacts following treatment discontinuation

 To explore the initial anti-tumor activity of GSK2857916 in subjects with relapsed/refractory MM in terms of time-to-event (TTE) endpoints (Part 2 MM) 	
 Time to progression (TTP), defined as: the time from first dose until the earliest date of PD per International Multiple Myeloma Working Group (IMWG), or death due to PD. Duration of response (DOR), defined as: the time from first documented evidence of PR or better; until the time when disease progression (PD) is documented per IMWG; or death due to PD occurs in subjects who achieve a response, i.e. confirmed PR or better. Time to response (TTR), defined as: the time between the date of first dose and the first documented evidence of response (PR or better), among subjects who achieve a response, i.e. confirmed PR or better. Time to best response (TTBR), defined as the time between the date of first dose and first documented evidence of the best response (PR or better), among subjects who achieve a response (i.e., confirmed PR or better). Progression-free survival (PFS), defined as: the time from first dose until the earliest date of disease progression (PD) per IMWG, or death due to any cause. Number of deaths.

2.3. Study Design

Overview of Study Design and Key Features	
Dosing	
 • Part 1 Dose Escalation Initially, GSK2857916 will be administered (IV) via 60 min infusion once every three weeks (21 days = 1 cycle) on Schedule 1. Once an MTD1 or RP2D has been established on the once every 21-day (Schedule 1), the safety, tolerability, PK, and PD of once-weekly dosing (Schedule 2) of GSK2857916 may be explored as an additional cohort(s). • Part 2: Dose Expansion Phase Subjects enrolled in Part 2 dose expansion phase will be administered GSK2857916 at recommended phase 2 dose (RP2D) established based on Part 1 outcomes.
Time & Events	
 • Refer to Appendix 2: Schedule of Activities
Treatment Assignment	
 • This is a non-randomized open-label study.
Interim Analysis	
 • Part 1: Dose Escalation Phase No formal interim analysis is planned for Part 1. Safety, pharmacokinetic and pharmacodynamic marker data will be examined on an ongoing basis to support dose escalation decisions. • Part 2: Dose Expansion Phase 
 ○ For MM cohort, one futility analysis based on ORR data was performed after approximately 30 subjects are evaluable (originally 3 futility analyses are planned after approximately 15, 22 and 30 subjects are evaluable). The number of confirmed responses (PR or better) observed will be compared with the stopping rules provided in Section 13.6.2 of the protocol. ○ For the lymphomas expressing BCMA cohort, no interim analyses will be performed, though consideration would be given to closing the cohort should the enrolment be stopped in the MM cohort.

2.4. Statistical Hypotheses / Statistical Analyses

No formal statistical hypotheses will be tested in Part 1. Analysis of the data obtained from Part 1 will only utilize descriptive methods. In Part1, dose escalation/de-escalation decisions will be informed by the Bayesian approach: N-CRM (Neuenschwander-Continuous Reassessment Method) [Neuenschwander, 2008]. Details of the N-CRM model used for this study is described in Section 3.1.1.

The assumption for ORR in part 2 MM cohort is:

The null hypothesis H_0 : $ORR \leq 20\%$

The alternative hypothesis H_A : $ORR \geq 40\%$.

No hypothesis testing is planned for part 2 MM cohort. The methodology utilized is based on the predictive probability of success if enrollment continues to 40 subjects [Lee, 2008]. The predictive probability design is similar to a Green-Dahlberg design in that it allows for early stopping for futility. The differences are that the predictive probability design allows for evaluation of stopping rules as often as after each subject, rather than at only two stages. While the two designs have similar type I and type II error rates, the

probability of early termination is greater with the predictive probability design. In this particular study, one futility analysis based on ORR data was performed after approximately 30 subjects are evaluable (originally 3 futility analyses are planned after approximately 15, 22 and 30 subjects are evaluable).

3. PLANNED ANALYSES

3.1. Interim Analyses

3.1.1. Part 1: Dose Escalation Phase

While no formal interim analysis is planned for Part 1, safety, pharmacokinetic and pharmacodynamic marker data will be examined on an ongoing basis to support dose escalation decisions. Prior to determining the GSK2857916 dose for the next cohort enrolled, exploratory analysis will be conducted to assess the relationship of GSK2857916 dose levels with safety, PK and PD parameters using all data from available cohorts.

Dose escalation/de-escalations decisions will take into account all available data, including but not limited to the safety parameters, PD and PK data of all cohorts assessed. Dose escalation/de-escalation decisions will be informed by the N-CRM (Neuenschwander-Continuous Reassessment Method) [Neuenschwander, 2008]. The N-CRM model used for Schedule 1 is described in detail in Section 3.1.1.1 and Section 3.1.1.2. The method is fully adaptive and makes use of all DLT information available at the time of each dose assignment.

3.1.1.1. Description of the New Continual Reassessment Method

The N-CRM is a type of Bayesian adaptive dose-escalation scheme that estimates the parameters of a statistical model relating dose and toxicity, and is expected to locate the MTD efficiently while minimizing the number of subjects exposed to pharmacologically inactive or unsafe dose levels. The method is fully adaptive and makes use of all the toxicity information available at the time of each dose assignment. N-CRM estimates may be provided at dose escalation meetings as supportive material to the primary 3+3 dose escalation design.

The N-CRM estimates, for each potential dose, the (Bayesian) posterior probabilities that the DLT rate lies in each of four predefined toxicity ranges:

- A dose falls in the **Under-dosing** range if the rate of a DLT at the dose is in the interval [0%, 16%).
- A dose falls in the **Target** toxicity range if the rate of a DLT at the dose is in the interval [16%, 33%).
- A dose falls in the **Excessive** toxicity range if the rate of a DLT at the dose is in the interval [33%, 60%).

- A dose falls in the **Unacceptable** toxicity range if the rate of a DLT at the dose is in the interval [60%, 100%].

Additionally, the following over-dose constraints for the recommended dose will be maintained:

- The posterior probability of the DLT rate lying in the Excessive Toxicity or Unacceptable Toxicity range is 0.25 or less.
- The recommended dose is no more than 2 times that of the previous dose.
- Note that a de-escalation recommendation is possible using this method. At the time of each dose-escalation decision, the dose with the highest posterior probability of lying in the Target Toxicity range (subject to the given constraints) will be the model-recommended dose for the next cohort.

The N-CRM procedure for Schedule 1 will utilize a single subject/cohort run-in phase.

The single subject (small cohort) run-in will be halted when the first \geq Grade 2 toxicity for which relationship to the investigational agent cannot be ruled out occurs in one subject in Cycle 1 (21 days). At this point, the cohort will be expanded to 3 or more subjects at the same dose level and the escalation will continue to follow the N-CRM procedure as outlined in [Table 2](#)

Table 2 Single Subject (Small Cohort) Run-In Procedure for GSK2857916 given on Schedule 1 (once every 21 days)

Dose Level	Number of subjects with \geq G2 toxicity	Dose Escalation/Action
Dose Level 1/Cohort 1	0 out of 1 subject (Sentinel subject)	Predicted starting dose 0.03 mg/kg every 21 days
Dose Level 2/Cohort 2	0 out of 1 subject	Escalate to the next dose level with increase \leq 100% of the starting dose
Dose Level 3 and beyond/Cohort 3 and beyond	0 out of 1 subject	Escalate to the next dose level with increase of \leq 100% of the dose tested in the previous cohort
	1 out of 1 subject*	Switch to Cohort size of 3 or more subjects

*Increase of doses **up to** 100% of the previous dose may continue until the first \geq Grade 2 toxicity for which relationship to the investigational agent cannot be ruled out occurs in one subject in Cycle 1 (21 days). At this point the single subject (small cohort) run-in is halted. Continue with N-CRM, with cohort sizes of 3 or more subjects. Increase of doses \leq 100% will be considered for subsequent cohorts of 3 or more subjects.

3.1.1.2. Prior Probability Distribution

Elicited prior probabilities of a DLT at each dose were used to determine the prior distribution of the parameters of an explicit logistic dose-toxicity model, namely

m,

where p_d is the probability of a DLT at dose d , and d_m is a reference dose.

The prior distribution of $(\alpha, \ln(\beta))$ will be assumed to be bivariate normal with means (standard deviations): $E[\alpha]=-1.3281$ (1.7153), $E[\ln(\beta)]=-0.795$ (1), with correlation between α and $\ln(\beta)$ set to $\rho=-0.9352$ and $d_m=0.72$ mg/kg.

3.1.1.3. Displays To Be Created For Dose Escalation Review

Review of preliminary data will be performed after completion of each dosing cohort in Part 1. Preliminary safety and study population data may include a demographic summary, adverse event (AE) summary, AE summary by maximum toxicity category, SAE listing, listing of AEs that are reported to be DLT's, and listing of AEs leading to dose modification. Spreadsheets containing relevant study data may also be supplied by the study data manager.

Further, after single subject run-in was halted, after each expanded cohort in dose escalation, the recommended dose from the N-CRM method and updated posterior estimates of the probabilities of being in each dose-toxicity range may be provided. The Fixed and Adaptive Clinical Trial Simulator (FACTS) (Version 2.4 or higher) software from Tessella will be used to make N-CRM calculations.

Prior to determining a dose for the next cohort, exploratory analyses will be conducted to assess the relationship of dose levels with safety, PK, and pharmacodynamic parameters using all data from available cohorts.

The GSK study team, in collaboration with study investigators, will review all relevant data to support:

- whether the current dose had acceptable toxicity, and
- the decision regarding the next dose level based on the totality of the data

3.1.2. Part 2 Expansion Phase

3.1.2.1. Multiple Myeloma Expansion Cohort

During Part 2 (Expansion Cohort), futility analyses of response data will be conducted in order to determine whether the futility criteria for stopping have been met. The study will not be stopped early for efficacy, but is designed to stop early for futility if the predictive probability of success is less than 5%.

For Multiple Myeloma cohort, response data will be reviewed once approximately 30 subjects are evaluable at the RP2D dose and the number of confirmed responses (PR, VGPR, CR, and sCR) will be compared with the stopping rules provided in [Table 3](#) based on predictive probability design of Lee et al. [[Lee, 2008](#)].

In addition to considering the recommendations of the futility analyses, final decisions on stopping enrolment in the MM cohort will depend on the totality of the data collected. Should the recommendation to stop for futility be disregarded in favour of a decision to

continue the trial based on the totality of the data, the overall type I error rate of the expansion phase will be inflated.

Table 3 Futility Stopping Region for Multiple Myeloma Expansion Cohort

Number of Evaluable Subjects	Number of Overall Responses												
	0	1	2	3	4	5	6	7	8	9	10	11	>11
15													
16													
17													
18													
19													
20													
21													
22													
23													
24													
25													
26													
27													
28													
29													
30													
31													
32													
33													
34													
35													
36													
37													
38													
39													
40													

3.1.2.1.1. Operating Characteristics of the Stopping Rules for Futility

The stopping rule in Table 3 is based on the methodology of Lee et al. [Lee, 2008]. For the MM expansion cohort, starting with 15 subjects and allowing for a maximum sample size of 40, this design will have a type I error rate of 0.075 and 89.8% power. Under the null hypothesis, if the true response rate is 20%, the expected sample size of the design is 23.4 subjects and probability of early termination (PET) is 88.9%. Under the alternative hypothesis, if the true response rate is 40%, the expected sample size of the design is 38.6 subjects and probability of early termination (PET) is 8.5%.

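### The MM futility operating characteristics in SAP 3.1.2.1.1 assume a look after every subject from 15 on, not the single look at about 30 that the plan uses

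*SAP*

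**What the plan says.** Section 3.1.2.1.1 describes the Table 3 rule as "starting with 15 subjects and allowing for a maximum sample size of 40" and says "this design will have a type I error rate of 0.075 and 89.8% power". It continues: "Under the null hypothesis, if the true response rate is 20%, the expected sample size of the design is 23.4 subjects", with a PET of 88.9%. At 40% it gives 38.6 and 8.5%. It does not say how often the rule is assumed to be applied.

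Section 2.4 says that in this study "one futility analysis based on ORR data was performed after approximately 30 subjects are evaluable", and adds that three looks, at about 15, 22 and 30 subjects, had been planned. The interim analysis row of Section 2.3 says the same.

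Section 3.1.2.1 says "response data will be reviewed once approximately 30 subjects are evaluable at the RP2D dose". The word *once* there may mean *as soon as*, and that section also speaks of futility analyses in the plural, so Sections 2.3 and 2.4 are the clear support for a single look. Section 3.1.2.1 also sets the threshold: the study is "designed to stop early for futility if the predictive probability of success is less than 5" per cent, with no early stop for efficacy.

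Table 3 has a row for every sample size from 15 to 40.

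**The concern.** The number of looks was changed in Sections 2.3 and 2.4, but the properties in Section 3.1.2.1.1 do not reflect the change. They are the only operating characteristics the SAP gives for this cohort. A study report that repeats them would credit the design with an expected size it cannot have, and with a much better chance of stopping early for an inactive treatment than one look at about 30 provides.

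**Working it through.** **Step 1: a check that needs no assumption.** With one look at n and a maximum of 40, E(N) = n × PET + 40 × (1 − PET). For n near 30 this lies between about 30 and 40, so 23.4 is out of reach. The SAP's own null pair also gives the average size at which stopped trials stop: (23.4 − 40 × 0.111) / 0.889 = 18.96 / 0.889 = 21.3. That is well below 30.

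**Step 2: inputs.**
- From the SAP: null rate 20% and alternative rate 40% (Section 2.4); first look at 15 and maximum 40 (Section 3.1.2.1.1); stop when predictive probability is below 5% (Section 3.1.2.1).
- Assumed: success at 12 or more responses of 40, and a Beta(0.2, 0.8) prior. The text at hand gives neither, and the shading of Table 3 is not readable in it.

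**Step 3: reproduce the SAP's figures.** After x responses in n subjects, the predictive probability is the beta-binomial probability of at least 12 − x responses among the remaining 40 − n, with posterior Beta(0.2 + x, 0.8 + n − x). An exact binomial recursion then gives:

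| Quantity | SAP | Every subject, 15–39 | Looks at 15, 22, 30 | One look at 30 |
|---|---|---|---|---|
| Type I error | 0.075 | 0.0754 | 0.080 | 0.086 |
| Power | 89.8% | 89.75% | 90.8% | 92.7% |
| PET at 20% | 88.9% | 88.85% | 68.3% | 60.7% |
| E(N) at 20% | 23.4 | 23.42 | 25.7 | 33.9 |
| PET at 40% | 8.5% | 8.49% | 4.6% | 1.7% |
| E(N) at 40% | 38.6 | 38.64 | 39.0 | 39.8 |

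Per-subject monitoring agrees with all six stated figures to within rounding; the largest gap is 0.05 of a percentage point, in null PET. The other two schedules do not fit.

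**Step 4: the single look by hand.**
- Boundary: at 6 of 30, at least 6 of the last 10 must respond, and the predictive probability is 0.016, so stop. At 7 of 30 at least 5 of 10 are needed and it is 0.086, so continue. The rule is to stop at 6 or fewer.
- PET = P(X ≤ 6 of 30): 0.607 at 20% and 0.017 at 40%.
- E(N) = 40 − 10 × PET: 40 − 6.07 = 33.9 and 40 − 0.17 = 39.8.
- Type I error = P(X ≥ 12 of 40) less the part lost to stopping: 0.0875 − 0.0013 = 0.0862. Power: 0.929 − 0.002 = 0.927.

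**Step 5: sensitivity of the single look.**
- Look anywhere from 28 to 32: type I 0.085–0.087, power 92.5–92.8%, null PET 50–70%, null E(N) 32.9–34.9, PET at 40% 1.1–2.5%.
- Prior: the boundary at 30 is 6 for every prior tried with cut-off 12. The prior is not uniquely identified, since Beta(0.1, 0.4) gives the same per-subject results.
- Cut-off 11: type I 0.160, null PET 42.8%, null E(N) 35.7. Cut-off 13: 0.042, 76.1%, 32.4. Neither cut-off reproduces the stated set.

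**The case against.** The strongest reply is that nothing in the planned analysis rests on these figures. Section 2.4 plans no hypothesis test for this cohort, Section 7.1 has no primary efficacy analysis, and ORR is reported with an exact 95% interval. The futility look is described as already performed, and Section 3.1.2.1 leaves stopping to the totality of the data. All of this stands, and it limits the consequence: a correction changes no estimate, interval or pending decision.

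It can also be said that Section 3.1.2.1.1 describes the Table 3 rule from 15 subjects on, and so is partly labelled. That stands only in part. The paragraph never says a look after each subject is assumed, and Section 2.4 presents per-subject evaluation as something the method permits, not as what this study did.

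Two stronger readings are tempting. One is that the sponsor miscalculated; it did not, because the figures are correct for per-subject monitoring. The other is that false-positive risk is seriously understated. The documents do not support that: type I error goes from 0.075 to about 0.086, it would be only 0.0875 with no futility look at all, and no test is planned.

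**Conclusion.** The point holds as an internal inconsistency. The impossibility of a null expected size of 23.4 with a first stop near 30 rests on nothing beyond the SAP's own text.

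The size of the discrepancy rests on the inferred cut-off of 12 of 40 and on the prior. The evidence for them is that together they recover all six stated figures to within rounding. On that footing the main error is overstated futility protection: null PET is about 61%, not 88.9%, and null expected size about 34, not 23.4. Type I error is slightly understated. Power is understated too, at about 92.7% against 89.8%, so the correction is not all in one direction. The single-look values are indicative and do not replace the sponsor's own calculation.

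**What to change.** Rewrite the paragraph in Section 3.1.2.1.1 for one look at about 30 evaluable subjects. The sponsor should compute the figures from its actual Table 3 boundary and success cut-off, state both, and give a range to reflect that the look was at approximately 30. If the present figures are kept, label them as assuming a look after every subject from 15 on.

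If the inferred inputs are confirmed, the entries are about: type I error 0.086, power 92.7%, PET 61% and 1.7%, and expected size 33.9 and 39.8 at response rates of 20% and 40%.

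The cost is one paragraph and a short calculation. Type I error, null PET and both expected sample sizes become less favourable; power and PET at 40% improve.
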